## Participants

The children that we include in our sample are those who meet the following criteria.

- They are referred to the local authorities' children's services. This is a rather broad baseline population which we use because the implementation of Family Safeguarding can potentially lead to changes in assessment thresholds.
- Their original referral date falls within the trial period as defined above.
- Are aged 0-12 at the time of referral. This is the primary age group that the Family Safeguarding teams in the developer local authority Hertfordshire work with. While Safeguarding teams can in theory work with adolescents as well, safeguarding concerns among adolescents are more likely to become contextual which in some local authorities are specifically addressed by adolescent teams. Since the Family Safeguarding model also focuses on work with parents, the implementation is likely to have a larger effect on children up to the age of 12 than on young people.

This will provide our analytical sample, which will then be further restricted or extended for different outcomes, as described in the RCT Design Table above and in the 'Outcome measures' section below.

## Conditions

Children that form part of the samples described above will be designated as part of the treatment and control groups according to whether Family Safeguarding was implemented in their local authority at the time of their first referral start date in the trial period. This date also marks the starting point from which we measure any outcomes over the periods of time defined in the RCT Design Table above. Compared to other possible dates at a later stage in the referral, this constitutes a conservative approach. Some children in the control group might have been in contact with Family Safeguarding teams at a later stage of their referral which can bias our estimate downwards. We revisit this approach in our sensitivity analysis.

We only consider referrals that started during or after our baseline period and do not allow children to enter our sample twice i.e. any additional referrals after the first referral in the trial period defining our baseline population will not lead to additional entry into the sample, though the consequences of subsequent referrals may affect the outcome coding.

For Secondary Outcome 5 - Repeat referrals for domestic violence, mental health or substance misuse - we alter our definition of treatment and control. Here, the relevant referral date will be the first referral in the trial period, where the following assessment identified one of the three factors at the end of assessment. This is because some activities of Family Safeguarding such as specialist adult practitioners only focus on children in this subgroup. Thus, any referrals prior to this, where the assessment following a referral did not identify one of these factors at the end of assessment, will be disregarded.

Conditions Table		
Condition	Primary Outcome and Secondary Outcomes 1-4 & 6 definition	Secondary Outcome 5 definition
Control	Children whose first referral in the trial period took place when the local authority was running their business as usual model.	Children whose first referral in the trial period - where the factors identified at the end of assessment included either parental substance misuse, parental mental health, or domestic violence - took place when the local authority was running their business as usual model.
Treatment	Children whose first referral in the trial period took place when the local authority was running the Family Safeguarding model.	Children whose first referral in the trial period- where the factors identified at the end of assessment included either parental substance misuse, parental mental health, or domestic violence - took place when the local authority had implemented the Family Safeguarding model.

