## Context

The IPE and RCT parts of the evaluation will be undertaken in the local authorities funded by the Department for Education to introduce Family Safeguarding as part of the Strengthening Families, Protecting Children programme, with the exception of the Trailblazer who is participating in a separate pilot evaluation. These local authorities are due to launch Family Safeguarding at six-month intervals beginning in April 2020. In the order they will be rolled out, these local authorities are Walsall, Lancashire, Telford & Wrekin, Wandsworth and Swindon.

All authorities had a judgement of ‘requires improvement to be good’ at the point at which they applied for the programme. However, at the point of rollout to the first local authority, Children’s Services in three of these authorities (Walsall, Lancashire and Wandsworth) have an Ofsted judgement of ‘requires improvement to be good’, while Swindon received a

judgement of 'good' in July 2019 and Telford & Wrekin received a judgement of 'outstanding' in January 2020. These authorities were selected by the Department for Education to participate in the programme due to having high rates of children looked after compared to their local authority statistical neighbour median over the last 3 years, and/or rising rates of children looked after in each of the last 3 years.

York Consulting is currently conducting a process evaluation of Family Safeguarding in four additional local authorities, namely Peterborough, Luton, Bracknell Forest and West Berkshire.

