For the purposes of this RCT, we will only consider children who have been in touch with children's social care between six-months before the first local authority's implementation date, and six-months after the last local authority's implementation date. We define the implementation date as the date the Family Safeguarding model is considered 'Operationally Live' in the local authority. The Operationally Live date has been set in advance by the Department for Education. When analysing the data, we may change the date we consider the intervention to have gone Operationally Live, if it becomes apparent that there have been significant changes in terms of the timings of the models core activities. This will only be done with the agreement with the Department for Education and consultation with the model developer. Any such changes will be detailed in the report. Specifically, the core activities are as detailed below.

[figure not shown]
By the Operationally Live date:

- Training in Motivational Interviewing and workshops by the model developers should have been delivered to all staff in family safeguarding teams.
- Specialist adult workers should be recruited and in post.

From the Operationally Live date:

- Staff should be using Motivational Interviewing and the parenting assessment and intervention programme with families,
- Staff should be recording case notes using the electronic workbook
- Group case supervision should begin taking place at regular intervals for cases with adult specialist worker involvement.

The diagram below illustrates the randomisation and intended timings of the implementation of Family Safeguarding across the local authorities. The trial period, as indicated in the diagram, takes place from 6 months prior to when the first local authority implements the model (or goes Operationally Live), and continues until 6 months after the final local authority implements the model.

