There is a risk of non-compliance, e.g. local authorities may implement some or all aspects ahead of their agreed Operationally Live date, or fail to implement some elements. As stated above, we will adjust the date we consider Family Safeguarding has been implemented, if it

---

 Population as described above.

 We consider the referral date to be the relevant date according to which the relevant time dummy is determined.

 Children can only occur once in our evaluation, i.e. that we consider the first referral.

becomes apparent that there have been significant changes in terms of the timings of the models core activities. This will only be done with the agreement of the Department for Education and in consultation with the model developer. However, outside of this we will take an intention-to-treat approach, and will not, in our primary analysis consider other elements of non-compliance. However if the IPE shows that there have been substantial instances of non-compliance, we will consider running complier average causal effect (CACE) analysis to account for this. This would however be secondary analysis.

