#### Vector of individual level covariates of the child or young person

- Gender (included as a binary indicators for male, female, or other/undetermined)
- Ethnicity
- Age in months
- Academic year
- Disabled status (included as a binary indicator: 0=No, 1= Yes)
- Eligibility for free school meals (included as a binary indicator: 0=No, 1=Yes, if pupil has ever been recorded as eligible for free school meals on Census day in any Spring Census up to the pupil's current year), Pupil Premium eligibility (for Reception, Year 1 and Year 2)
- Is child an Unaccompanied Asylum Seeker (included as a binary indicators, 0=No, 1= Yes)
- Number of previous child protection plans
- The main need for which child started to receive services for this referral (if applicable), as defined in the [CIN census](#) (included as a categorical variable: 0 = Not stated, 1 = Abuse or neglect, 2 = Child's disability/illness, 3 = Parental Disability/illness, 4 = Family in acute stress, 5 = Family dysfunction, 6 = Socially unacceptable, 7 = Low income, 8 = Absent parenting, 9 = Cases other than Children in Need).

In addition, we would have wanted to take into account families (e.g. through adding family fixed effects), however we are reasonably confident data will not be available, so we have refrained from including them.

---

 In the categories defined in the DfE's CIN census.

 We use Pupil Premium Eligibility for the first three years as every child is eligible for free school meals during this period.

 UN High Commissioner for Refugees (UNHCR). (2013, March). *UNHCR's Engagement with Displaced Youth*. <https://www.refworld.org/docid/5142d52d2.html>, p28.

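### The look-back behind a child's first referral lengthens from 0-6 to 30-36 months across the steps, and the case-mix drift that differs between authorities is not adjusted for

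*Protocol*

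**What the plan says.** The Protocol's Randomisation section says that the trial period "takes place from 6 months prior to when the first local authority implements the model" and "continues until 6 months after the final local authority implements the model". Context says that authorities are "due to launch Family Safeguarding at six-month intervals beginning in April 2020". Five launches give six steps and 36 months.

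Participants requires of each child: "Their original referral date falls within the trial period as defined above". Conditions adds "We only consider referrals that started during or after our baseline period and do not allow children to enter our sample twice", and then "any additional referrals after the first referral in the trial period defining our baseline population will not lead to additional entry into the sample". A footnote to the Primary Analysis repeats this: "Children can only occur once in our evaluation, i.e. that we consider the first referral". Condition is set by whether the model was live at that referral. No referral-free run-in or common look-back is defined.

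The primary model has dummies for the five steps after baseline, a random intercept per authority, child covariates and time-varying authority covariates. In the child list, the item on earlier contact with services is "Number of previous child protection plans". No covariate records an earlier referral.

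**The concern.** In step 0, a child referred a month before the trial opened still enters as a first referral. In step 5, a child with any referral in the preceding 30 or more months has already been counted and cannot enter. The same rule therefore selects different populations at different times. Control observations come mainly from early steps and treated observations from late ones.

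If repeat-referred children are more likely to enter care, risk in the analysed sample falls over time with no change in practice. Period dummies absorb that fall only as far as it is the same everywhere. An authority with many re-referrals loses such children faster than one with few, and neither a common dummy nor a constant authority intercept can follow that difference. Any remainder enters the treatment coefficient, for the primary outcome and for the secondary outcomes that share the entry rule. Secondary Outcome 5 uses a similar first-in-trial rule.

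A second consequence holds even with no bias: the treated evidence comes from children with fewer recent referrals than the control evidence.

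**Working it through.** **1. The plan's own figure.** Inputs from the MDES table and Appendix B: I = 5 authorities, T = 6 periods, m = 1,700 per cell, p = 0.06, ICC 0.00722, two-sided 5%, 80% power.

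- Hussey-Hughes variance: I s²(s² + T t²) / [(IU - W)s² + (U² + ITU - TW - IV)t²].
- s² = 0.0564 × (1 - 0.00722)/1,700 = 3.294e-5; t² = 0.00722 × 0.0564 = 4.072e-4.
- U = 15 and W = V = 55, so the bracketed coefficients are 20 and 70.
- Variance = 4.078e-7 / 0.02916 = 1.398e-5, so SE = 0.374 pp.
- MDES = (1.960 + 0.842) × 0.374 = 1.05 pp, as stated.

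**2. Look-back by step (document figures only).**

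| Step | 0 | 1 | 2 | 3 | 4 | 5 |
|---|---|---|---|---|---|---|
| Mid-step look-back, months | 3 | 9 | 15 | 21 | 27 | 33 |
| Control authorities | 5 | 4 | 3 | 2 | 1 | 0 |
| Treated authorities | 0 | 1 | 2 | 3 | 4 | 5 |

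- Control mean: (5×3 + 4×9 + 3×15 + 2×21 + 1×27)/15 = 165/15 = 11 months.
- Treated mean: (1×9 + 2×15 + 3×21 + 4×27 + 5×33)/15 = 375/15 = 25 months.
- Cells with at least 12 months: 6 of 15 control (40%), 14 of 15 treated (93%).
- Within one step, control and treated cells have identical look-back.

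**3. What survives the period dummies.** The documents give no re-referral rate, excess risk or between-authority spread. The following are assumptions.

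- Share r of referred children with another referral in the previous 12 months: 15% to 30%, varying between authorities. The share with one in the previous L months is S(L) = 2r(1 - 2^(-L/12)), a 12-month half-life.
- Share of the step-t sample with a referral in the previous 33 months: q = (S(33) - S(L))/(1 - S(L)).
- Cell risk is proportional to 1 + (RR - 1)q, scaled so that each authority starts at the plan's 6% in step 0. There is no treatment effect.

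At RR = 2 the cell rates (%) are:

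| Step | 0 | 1 | 2 | 3 | 4 | 5 |
|---|---|---|---|---|---|---|
| r = 15% | 6.000 | 5.676 | 5.412 | 5.204 | 5.045 | 4.926 |
| r = 30% | 6.000 | 5.566 | 5.140 | 4.746 | 4.401 | 4.112 |
| Difference | 0 | -0.110 | -0.272 | -0.458 | -0.644 | -0.814 |

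The generalised least squares weights behind the SE in step 1 sum to zero over authorities in every step, so only the difference row matters. The worst case has 30% in the first and last authorities to launch and 15% in the middle three. The weights of those two positions add to 0, 0.255, 0.085, -0.085, -0.255, 0. Bias = 0.255(-0.110) + 0.085(-0.272) - 0.085(-0.458) - 0.255(-0.644) = +0.15 pp. Swapping the two rates gives -0.15 pp.

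Over all assignments of 15, 20, 25 and 30% to the five launch positions:

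| Risk ratio | Mean bias | Root mean square | Extremes |
|---|---|---|---|
| 1.5 | 0 | 0.03 pp | ±0.10 pp |
| 2 | 0 | 0.05 pp | ±0.15 pp |
| 3 | 0 | 0.07 pp | ±0.20 pp |

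At risk ratio 2 that is 0.05/0.374, about 0.14 SE, typically, and 0.15/0.374, about 0.41 SE, at most. Roughly half of the assignments give less than 0.1 SE.

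**4. Sensitivity to the scaling.** If the 6% is instead given to children without an earlier referral in every authority, the extremes at risk ratio 2 widen to about ±0.26 pp. Step-0 rates would then be 7.3% to 8.8% (6 × 1.218 and 6 × 1.459), which no longer match the plan's baseline.

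**The case against.** A reader might infer that repeat-referred children fill the control cells and vanish from the treated cells, so that the model looks beneficial by construction. The documents do not support that. Thinning follows calendar time, not condition: late control cells are thinned as much as treated cells in the same step, and early treated cells keep many repeat-referred children. With the planned period dummies the adjusted bias is zero if depletion is equal across authorities. A crude control-versus-treated contrast is something the plan never estimates.

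The remainder is also modest. It has no expected direction, averages zero over all assignments of rates to launch positions, vanishes if repeat-referred children carry no excess risk, and is negligible for many unequal patterns. Age, main need, previous plans and the time-varying authority covariates may absorb some of it. Every input on re-referral is assumed.

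All of this stands, and it limits the point to a refinement. It does not remove it, because the trial has one realised order of five authorities. The order is also constrained: the two high-readiness authorities must come first, so only 2! × 3! = 12 orders were possible and averaging over every assignment is generous. If both high-readiness authorities had a 30% rate and the other three 15%, the bias at risk ratio 2 would be about 0.05 pp in all 12. A previously referred child who never had a plan scores zero on the listed history covariate. The alternative treatment definitions under Sensitivity Analysis change exposure coding and leave the entry rule as it is.

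**Conclusion.** The concern holds in limited form. That the look-back grows, and averages 11 months in control cells against 25 in treated cells, follows from the text alone. The period dummies remove the common part. Authority-specific drift is left without adequate adjustment and could move the primary coefficient either way. Under the stated assumptions this is typically about 0.05 pp and at most about 0.15 pp at risk ratio 2 (0.10 pp at 1.5, 0.20 pp at 3), against an SE of 0.374 pp and an MDES of 1.05 pp. It would not overturn a clear result, but it could shift a borderline one. Separately, the report should say that the treated evidence under-represents children with recent earlier referrals.

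**What to change.** In the individual-level covariate list, add prior referral measured over one fixed look-back before the index referral, the same in every step and taken from authority records that predate the trial. A window of 36 months would match the longest in-trial look-back. Record whether there was any referral in the window and the time since the last one. For children younger than the window, use history since birth; age is already in the model. Include the covariate in the primary and secondary models.

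Add a sensitivity analysis restricted, in every step, to children with no referral in that window, so that a first referral means the same thing throughout and the 14-month difference in mean look-back (25 - 11) becomes zero.

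The cost is one extra field, the date of the last previous referral, in a data request that is already planned, with extraction reaching back before the trial. The plan limits requests to data held for statutory returns, so availability should be confirmed before the template is final. The restricted analysis will have smaller cells in the early steps.

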## Outcome measures

For the trial we will evaluate one primary outcome measure and six secondary outcome measures. Individual level data will be collected directly from the five local authorities participating in the Family Safeguarding trial, detailed above. Below we give an explanation

and rationale of the outcomes outlined in the RCT Design Table. In the instance of any unintentional inconsistencies, the above table definitions should take precedent in the analysis.

### ***Primary outcome measure***

#### **Whether or not the child has become looked after**

To answer research question 1, we will analyse whether children (aged 0 - 12 who are referred to Children's Social Care within the trial period) are more or less likely to become looked after within 18 months of starting the referral where Family Safeguarding had been implemented, compared to when it had not been. The outcome measure is a binary variable, indicating whether or not a child that is in our sample (defined above) has become looked after at any point within 18 months of their first referral in the trial period.

### ***Secondary outcome measures***

In addition to the primary outcome, we will also seek to evaluate six secondary outcome measures.

#### **Whether or not the child has returned to statutory services, following a CPP**

To answer research question 2, we use a binary outcome measure, indicating whether or not the child has returned to statutory services within 36 months of the initial referral start date, having had a CPP closed following the initial referral start date. Our sample will include any child aged 0-12 that has had a referral within the trial period.

This outcome will seek to act as a measure for the quality of assessment and direct work with children and their families. We choose return to statutory services (rather than considering CPPs only) as our outcome measure to avoid classifying children whose needs have escalated to e.g. going into foster care as "non-returners". We acknowledge that we do count children that stay on CPPs as non-returners. If implementing Family Safeguarding changes the allocation of children to CIN and CP plans, this will further affect the measure. Thus care must be taken interpreting this outcome measure.

#### **CPP plan duration**

To answer research question 3, we use two different models. First, we will use a discrete variable measuring the number of days that the child has been on a single CPP, over a period of 24 months from the start of the CPP and censored for larger values. Our sample

---

 Note that the episode of care does not have to result directly from the initial referral, e.g. a child who had a case that was closed but then returns to children's services and becomes looked after within 24 months of the initial referral date will be coded as 1.

 We use the referral start date as the starting point for the 24 months time frame (as opposed to imposing a time frame starting from the end of the first CPP) to reduce potential endogeneity through selection into the sample. Endogeneity can occur if social workers assess risk differently through Family Safeguarding. This might lead to a change in the length of CPPs, which in turn can result in different children in treatment and control groups terminating a first CPP within the trial period.

 that is, any values over 24 months will be coded as 24 months.

will include any child aged 0-12 that has had a referral within the trial period that led to a child protection plan (CPP) within 12 months of the referral start date.

### **Days on CPPs**

Second, we will use a discrete variable measuring the number of days spent on CPPs in days. In this case we will use our full analytical sample, i.e. all children that have been referred within the trial period. Thus any children who are not on any CPPs for the time frame of 36 months since the initial referral will be coded 0. We will record days spent on any CPP within that period i.e. multiple CPPs will be considered if applicable. Again, values over 36 months will be censored.

The potential reasons for changes in the time children spend on child protection plans are numerous. Spending longer on a CPP could be an indicator of children's social care providing additional support to a child and family so as to meet their needs. However, it might also be a sign of a child and family not having their needs adequately addressed in a timely manner. Thus it is hard to unambiguously interpret changes in this measure as either good or bad. Results will require careful interpretation in combination with the other outcome measures, and findings from the accompanying implementation and process evaluation.

